**National Institute of Diabetes and Digestive and Kidney Diseases of the National Institute of Health**

The Careful Urinary Tract Infection Evaluation (CUTIE) study is an ancillary study under the Randomized Intervention for Children with Vesicoureteral Reflux (RIVUR) clinical trial. The CUTIE study protocol is similar to the RIVUR study with the exception that it is an observational study that did not assign treatment arms and the participants did not have vesicoureteral reflux (VUR).

CUTIE based all of its documentation on the RIVUR materials. All aspects of the RIVUR trial that were not applicable to the CUTIE study are crossed out in the manual of operations (MOP) and on the case report forms (CRFs).

**ABBREVIATIONS AND DEFINITIONS OF TERMS**

UTI	Urinary tract infection
Febrile UTI (FUTI)	
FUTI requires the presence of (1) fever, (2) pyuria based on urinalysis, and (3) culture-proven infection with a single primary organism^2. Specifically, the study definition of FUTI requires:
 
I. Fever
 
 
• Documented temperature of at least 100.4 °F or 38°C, measured anywhere on the body either at home or at doctor's office
 
 
AND
 
II. Pyuria on urinalysis
 
 
• >10 WBC/mm^3 (uncentrifuged specimen) OR
 
• >5 WBC/hpf (centrifuged specimen), OR
 
• Any level of positivity of leukocyte esterase on dipstick
 
 
AND
 
III. Culture proven infection with a single primary organism^2
 
 
• >5 x 10^4 CFU/mL (catheterized or suprapubic aspiration urine specimen) OR
 
• >10^5 CFU/mL (clean voided specimen)
 

Symptomatic Non-febrile UTI (sUTI)	
sUTI requires the presence of (1) urinary tract symptoms, (2) pyuria on urinalysis, and (3) culture-proven infection with a single primary organism^2. Specifically, the study definition of sUTI requires:
 
I. Symptoms
 
 
• Suprapubic, abdominal, or flank pain or tenderness, or urinary urgency, frequency, or hesitancy, or dysuria, or foul smelling urine, or in infants ≤ 4 months old, failure to thrive, dehydration, or hypothermia
 
 
AND
 
II. Pyuria on urinalysis
 
 
• >10 WBC/mm^3 (uncentrifuged specimen) OR
 
• >5 WBC/hpf (centrifuged specimen), OR
 
• > Any level of positivity of leukocyte esterase on dipstick
 
 
AND
 
III. Culture proven infection with a single primary organism^2
 
 
• >5 x 10^4 CFU/mL (catheterized or suprapubic aspiration urine specimen) OR
 

---

 Must occur within ± 24 hours of initiating work-up for UTI.

 Index UTI culture may also include 1 additional secondary organism with colony count <10,000 CFU/mL (<10X10^3)

---

	
 
• <math>>10^5</math> CFU/mL (clean voided specimen)
 

Febrile or Symptomatic UTI (FSUTI)	As defined above in Febrile UTI (f-UTI) and Symptomatic Non-febrile UTI (sUTI)
Index UTI	
UTI that leads to VCUG and patient recruitment for the study.
 
The index UTI may be either:
 
(1) The participant's first febrile or symptomatic UTI OR
 
(2) The participant's second UTI which is either febrile or symptomatic, and where the first UTI did NOT result in either:
 
 
• the patient being placed on antimicrobial prophylaxis, or
 
• the diagnosis of VUR
 
 
Date of diagnosis for the index UTI is the date that the urine specimen that resulted in a positive culture was collected.

Recurrence of UTI	Infection more than 14 days after end of appropriate treatment of a UTI, or following a negative urine culture, or infection with a new organism.
Persistent UTI	Evidence of infection within 14 days after end of treatment of a UTI, in the absence of an intermediate negative urine culture (indicating that the treated UTI was never resolved).
Vesicoureteral Reflux (VUR)	VUR is defined as the retrograde flow of urine from the bladder up the ureter. It may or may not reach the level of the renal pelvis producing dilation of the upper urinary tract (see figure 5, section 3.1.2b)
VCUG	Voiding Cystourethrogram
Renal scarring (determined by DMSA)	Renal scarring will be defined as decreased uptake of tracer associated with loss of contours or cortical thinning. In order to quantify the extent of renal scarring, each kidney will be divided into 12 segments and a five level grading system will be applied. Severe scarring will be defined as the presence of grades 3 or 4 scarring on at least 1 kidney (see figure 7, section 4.1).
Dysfunctional voiding	A dysfunctional voiding symptoms score (DVSS) of more than 6 in female and more than 9 in male children $\geq 3$ years of age using a standardized scale  .
Chronic constipation in the toilet trained child, as defined by the Paris Consensus on Childhood Constipation Terminology (PACCT) Group 	
The occurrence of 2 or more of the following during the last 8 days in the toilet-trained child
 
 
• Frequency of bowel movement <math>< 3</math> / week
 
• More than one episode of fecal incontinence / week
 
• Large stools in the rectum or palpable on abdominal examination
 
• Passing of large stools that may obstruct the toilet
 
• Display of retentive posturing and withholding behaviors
 
• Painful defecation
 

Treatment failure:	
Treatment failure is defined by:
 
I. In any participant:

---

- Occurrence of 2 recurrent  $\text{F}_{\text{UTI}}$ s or a total of 4 recurrent  $\text{F}_{\text{SUTI}}$ s within the study period, OR
- Interim 12-month scan shows new or worsening scarring at a site different from the index APN or worsening scarring evidenced by extension of a preexistent scar seen on the baseline DMSA scan (note, the interim scan may serve as the outcome DMSA scan in these participants).

OR

- II. In children with baseline scarring grade 3 or higher:
  - Children whose initial DMSA scan shows grade 3 or higher scarring in either kidney will have a repeat DMSA performed at the time of any recurrent  $\text{F}_{\text{UTI}}$ ; if additional renal segment involvement is observed (APN or scar) compared with the baseline scan, then the child will be categorized as treatment failure and have an outcome DMSA scan at approximately 4 months following the  $\text{F}_{\text{UTI}}$ . If no additional renal segment involvement is observed, the child will continue in the study as assigned.

**Appropriately treated UTI**

Treatment for UTI will be considered appropriate if antibiotic therapy continues for a minimum of 7 days and:

- I. There is documented sensitivity of the organism to the antibiotic used for treatment OR
- II. There is a documented test of cure (negative urine culture) 1-14 days after completion of therapy.

**Society of Fetal Urology (SFU) grading of hydronephrosis**

- Grade 0 - No hydronephrosis, intact central renal complex.  
 Grade 1 - Only renal pelvis visualized. Dilated pelvis on ultrasound.  
 Grade 2 - Moderately dilated renal pelvis and few calyces seen.  
 Grade 3 - Hydronephrosis with nearly all calyces seen. Large renal pelvis and good parenchyma.  
 Grade 4 - Hydronephrosis with nearly all calyces seen and parenchymal atrophy or thinning.

---

**PROTOCOL SYNOPSIS**

---

**STUDY TITLE****SPONSOR**

National Institute of Diabetes and Digestive and Kidney Disease (NIDDK)  
National Institutes of Health (NIH)

**CLINICAL PHASE**

N/A

**STUDY RATIONALE**

Urinary tract infection (UTI) is the most common serious bacterial infection in young children. Estimates of cumulative incidence of UTI in children younger than 6 years of age (3-7% in girls, 1-2% in boys) suggest that 70,000 to 180,000 of the annual US birth cohort will have a UTI by age six. Approximately two-thirds of young children with febrile UTI will have acute pyelonephritis (APN), which involves infection and inflammation of the kidneys and ureters, and between 15 and 52 per cent of children with APN will develop subsequent renal scarring. The current standard of care for young children who present with UTI is to perform a voiding cystourethrogram (VCUG) to evaluate for the presence and degree of vesicoureteral reflux (VUR), a condition present in approximately 30-40% of children with UTI, in which urine flows retrograde during micturition from the bladder towards the kidneys. Until recently, it was widely accepted that VUR increased the risk of renal scarring from UTI, and so it was recommended that children with UTI and VUR have surgical correction of their VUR and/or receive daily antimicrobial prophylaxis to prevent UTI until the VUR resolves.

In recent years, our understanding of the relationship of UTI, VUR, and renal scarring, and current strategies for managing children with UTI have been challenged. It is now clear that renal scarring can occur in children who do not have VUR, and that most children who have even high grade VUR do not develop renal scarring. Analyses of dialysis and transplant registries suggest that the diagnosis and treatment of children with VUR that started in the 1960's have not been associated with a reduction in the incidence of end stage renal disease attributable to reflux nephropathy. Furthermore, older studies comparing the effectiveness of combined surgical correction and prophylactic antibiotics to prophylactic antibiotics alone, and more recent studies comparing prophylactic antibiotics to placebo, have shown no difference in rates of renal scarring, raising doubts about the significance of VUR in the progression to renal scarring, and the efficacy of either surgery or prophylactic antibiotics compared with prompt evaluation of urinary symptoms and early treatment of confirmed UTI.

In the fall of 2005 the NIDDK began funding a 5-year multicenter randomized placebo-controlled trial to evaluate the effectiveness and harms of prophylactic antimicrobials for the prevention of recurrent UTIs and renal scarring in children with VUR diagnosed after a first or second UTI (RIVUR—Randomized Intervention for Vesicoureteral Reflux; U01-DK074064). Because the goal of RIVUR is to evaluate the current paradigm of UTI management, which maintains that VUR is the main factor to be considered in determining which patients with UTI require antimicrobial prophylaxis, the study will enroll only patients who have VUR. However, the RIVUR protocol offers a unique opportunity to study the risks of renal scarring after UTI in children who do not have VUR. Three of the clinical trial centers participating in RIVUR will be recruiting patients at the time of UTI diagnosis (as opposed to after a diagnosis of VUR) and will be screening them for presence of VUR. By enrolling the children who do not have VUR into an ancillary study and following them for recurrence of UTI and development of renal scarring, we will be able to understand more completely the factors that place a child at risk for developing renal scarring, regardless of whether he/she has VUR.

---

Version 4.23.2008

Understanding which children are at the greatest risk of renal scarring after a UTI may allow us to provide more targeted therapies and interventions. Furthermore, by banking urine and blood from the children in both RIVUR and this proposed ancillary study, we create future opportunities to examine the genetic determinants of renal scarring in all children with UTI.

---

**STUDY OBJECTIVE(S)**
**Specific Aims:**

- 1) **To compare the proportion of children who develop renal scarring 2 years following a first or second episode of UTI among children in the proposed ancillary study who do not have VUR and children in the RIVUR study who do have VUR and are receiving placebo.**  
Hypothesis: The proportion of children who develop renal scarring among children in the ancillary study who do not have VUR and children in the RIVUR study who do have VUR and are receiving placebo will be equivalent (<10% absolute risk difference).
- 2) **To develop a prediction rule that accurately identifies children at high risk of developing renal scarring as well as children with virtually no risk of developing renal scarring following a first or second episode of UTI.**  
Hypothesis: A prediction rule incorporating clinical and demographic factors associated with renal scarring will predict with >98% sensitivity and >50% specificity which children will develop renal scarring following a first or second episode of UTI. A prediction rule with these test properties would identify nearly all children who develop renal scarring while accurately assessing as low risk at least 50% of children who do not develop renal scarring.

**Secondary Aims:**

- 1) **To compare the proportion of children who experience a recurrent UTI following the index UTI episode among children in the proposed ancillary study who do not have VUR and children in the RIVUR study who have VUR and are receiving placebo.**  
Hypothesis: The proportion of children who experience a recurrent UTI among children in the ancillary study who do not have VUR and children in the RIVUR study who do have VUR and are receiving placebo will be equivalent (<10% absolute risk difference).
- 2) **To develop a prediction rule that accurately identifies children at high risk of experiencing a recurrent UTI as well as children with virtually no risk for recurrence following a first or second episode of UTI.**  
Hypothesis: A prediction rule incorporating clinical and demographic factors associated with renal scarring will predict with >98% sensitivity and >50% specificity which children will have a recurrent UTI. A prediction rule with these test properties would identify nearly all children who go on to experience UTI recurrence while accurately assessing as low risk at least 50% of children who do not experience UTI recurrence.

---

**TEST ARTICLE(S)**  
*(if applicable)*

N/A

STUDY DESIGN	We propose to conduct a multi-center prospective cohort study comparing rates of renal scarring and recurrent UTI after a first or second UTI in 2 groups of children—one group of children who do not have VUR and one group of children who do have VUR and are treated as part of the RIVUR protocol with placebo. All participants will be enrolled over an 18-24 month period and followed for 2 years post-enrollment.
SUBJECT POPULATION	Inclusion Criteria
Main criteria for inclusion and exclusion:	
 
1) Age at enrollment 2-72 months. Note that children as young as 1 month may be screened for study.
 
2) Diagnosed first or second <math>F_{RS}</math>UTI within 112 days (16 weeks) prior to enrollment
 
3) Appropriately treated first or second <math>F_{RS}</math>UTI
 
4) Parental/guardian permission (informed consent) and if appropriate, child assent.
 

	Exclusion Criteria
	
 
1) For children less than 6 months of age at randomization, gestational age <34 wks
 
2) UTI diagnosis more than 112 days (16 weeks) prior to enrollment
 
3) Index UTI not appropriately treated
 
4) VUR (Grades I-V) diagnosis by VCUG
 
5) Co-morbid urologic anomalies
 
6) History of other renal injury/disease
 
7) Congenital or acquired immunodeficiency
 
8) Complex cardiac disease
 
9) Any known syndromes associated with VUR or bladder dysfunction
 
10) Unable to complete the study protocol
 
11) Unlikely to complete follow-up
 

NUMBER OF SUBJECTS	
Overall and at CHOP	360 overall; 120 at CHOP
Number of Study Sites	3
STUDY DURATION	
Duration subject participation	2 years
Expected Study Duration	4 years
STUDY PHASES	
Screening	2 years
Observation	2 years
EFFICACY EVALUATIONS	N/A
PHARMACOKINETIC EVALUATIONS (if applicable)	N/A
SAFETY EVALUATIONS	All subjects entered into the study at Visit 1 will be included in the safety analysis. The frequencies of AEs by type, body system, severity will be summarized. SAEs (if any) will be described in detail. This is an observational study and so we will report only AEs and SAEs directly related to the study and not to underlying illness.
STATISTICAL AND ANALYTIC PLAN	In order to test whether the proportion of children who have renal scarring on DMSA scan is equivalent among the ancillary study patients who did not have VUR and the placebo-treated RIVUR study who did have VUR, we will

---

calculate the difference in proportions and test whether the difference in proportions is less than 10% or not using a one-sided 0.05 significance level. We will therefore test the null hypothesis that the VUR group and non-VUR group are not equivalent and that the difference in the proportions of renal scarring between the groups is 10% or farther from zero in the same direction.

Multivariable modeling techniques will be used to develop prediction models for the development of renal scarring. Clinical judgment and strength of predictive variables in previous studies will force some variables to be included in the models regardless of their level of statistical significance (e.g., VUR grade, age, sex). Potential interaction variables to be considered in the models will be chosen based on the clinical judgment of the investigators and evidence from the literature, if both variables are candidates for inclusion in the model based on the first step

The analytic approach of (1) testing for equivalence of proportion of recurrent UTIs between patients who had VUR and were treated with placebo after their first or second UTI (RIVUR patients) and patients who did not have VUR after their first or second UTI (recruited as patients to this study) and (2) building a predictive model will be identical to the approach described above for the renal scarring outcome.

---

**DATA AND SAFETY  
MONITORING PLAN**

Because this is an observational study, we will not establish an independent Data and Safety Monitoring Board (DSMB) for this study. The site PIs will be charged with approving and/or making recommendations to the final draft of the protocol, as well as monitoring recruitment and retention and reviewing data for safety. Table 12 details the frequency and types of reports as part of this plan.

---

TABLE 1: SCHEDULE OF STUDY OBSERVATIONS AND PROCEDURES

Study Month Type of Contact	-2 to 0 (Visit) Screening	0 (Visit) Randomization/ Baseline	6 month (Visit) Follow-up	12 month (Visit) Follow-up	18 month (Visit) Follow-up	24 month (Visit) Follow-up	Every 2 months (Phone) Follow-up
Ultrasound	X*						
Contrast VCUG	X*						
Informed Consent	X						
DMSA		X**		†		X***	
Detailed Medical History		X					
Interim History		X	X	X	X	X	X
Physical Examination		X	X	X	X	X	
Questionnaires							
Dysf Void Symp Score and PACCT (age ≥3)		X		X		X	
Parent diary		X	X	X	X	X	X
QOL assessment		X		X		X	
Urine tests							
Urinalysis		X				X	
Culture		X††				X††	
Microalbumin/ Creatinine		X				X	
Urine for central Repository		X				X	
Blood tests							
Creatinine, lutes		X				X	
Cystatin C		X				X	
Blood for central Repository		X				X	
Telephone Follow-up							X

\*Screening ultrasound and VCUG may occur any time within 16 weeks following the index UTI as standard of care procedure.

[figure not shown]
\*\*Screening DMSA may occur within 2 weeks following randomization and no more than 16 weeks after the index UTI.

\*\*\*24 month DMSA scan may not occur if a study outcome scan has already been obtained.

†A DMSA scan will be performed at 1 year if there is an interim febrile UTI.

†† If urinalysis positive, culture is obtained

FIGURE 1: FLOW DIAGRAM FOR PROPOSED ANCILLARY STUDY

---

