#### 4.5 Outcome DMSA Scan

Outcome DMSA renal scans will follow the same procedures and standards of the baseline scan. In general participants will have the outcome DMSA scan performed 24 months after the index UTI. For safety reasons, we will use the criteria developed to define treatment failure for the RIVUR study as indications for performance of an early DMSA scan. Therefore, children whose baseline DMSA scan shows minimal or no scarring (grade 2 or less in each kidney) will have their outcome DMSA scan performed early if they experience the occurrence of 2 recurrent  $\neq$ UTIs or a total of 4 recurrent  $\neq$ UTIs within the study period. The outcome DMSA in these children will be performed approximately 4 months after the last UTI that qualified them as a "treatment failure". Children whose baseline DMSA scan shows grade 3 or higher scarring in either kidney will have a repeat DMSA scan performed at the time of any recurrent  $\neq$ UTI; if additional renal segment involvement (acute pyelonephritis or renal scarring) is observed, then, an outcome DMSA scan will be performed at approximately 4 months following any  $\neq$ UTI. If no additional renal segment involvement is observed, the child will have the outcome DMSA scan performed at 24 months per routine. Finally, children who have a febrile UTI in the first 8 months of the study will have an interim DMSA scan performed at 12 months. If new renal scarring is noted, that child will be considered a treatment failure and the interim DMSA scan will serve as the outcome scan. If a febrile UTI occurs within 8-12 months, the interim DMSA scan will be scheduled 4 months from the interim UTI.

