#### **7.4.5 The 12 Month Clinic Follow-up Visit**

The only differences between the 12 month follow-up clinic visit and other follow-up clinic visits (not including the end-of-study visit Section 7.4.6) are:

- All normal follow up forms including the FUP and CMF should be completed. If the child has received any medical care this should also be documented in the appropriate fashion.
- The self administered questionnaires, LIA Questionnaire (LIQ) and DV Questionnaire (DVQ) are administered. Refer to chapter 4: Enrollment and Baseline, section 4.5.3.

Participants who have a study endpoint (as determined by the Endpoints Committee) prior to the 12 month follow-visit, will have different scheduling criteria for their repeat DMSA. In this situation, the DCC will provide important information regarding any scheduling of repeat DMSA scans. All other data collection procedures for the 12 month clinic follow-up visit should proceed as documented above.

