#### **7.4.5.1 Scheduling the 12 month DMSA**

A DMSA scan will only be performed at 1 year if there is an interim febrile UTI.

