### **7.9.2 Early Study Endpoint Participants**

Participants who have had a study endpoint assessed by the Endpoints Committee will follow a different schedule for repeat DMSA imaging. The DCC will provide a report that notifies the Coordinator and Investigator of any endpoint determinations of treatment failure, and will provide instruction on the DMSA scheduling as specified in the protocol.

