#### **10.7.2 Identification of Treatment Failure**

The recurrence of a CUTIE study UTI is determined by either matching UCC classification records or the UCC adjudication process, and is based on data collected at the sites. The classification of UTIs must be very timely, as a determination of CUTIE UTI may result in a determination of treatment failure or the need for DMSA scheduling (for participant safety). Prompt completion of data entry forms and submission of source documentation to the DCC (if requested) will assure that such determinations can be made in timely manner.

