#### **10.7.3 Notification of Treatment Failures from DCC to the Sites**

UTIs determined by the UCC to be study endpoints will only be reported back to the clinical sites if the UTI now classifies the participant as a treatment failure, necessitating the discontinuation of study medication and/or scheduling of additional radiographic scans.

Once a UTI has been classified and it is determined that treatment failure criteria have been met, the DCC will send within 24 hours a memo via email to the site Principal Investigator (PI) notifying the PI that the participant has met treatment failure criteria, instructing the PI to discontinue study medication and refer the participant to standard care, and giving further instruction as necessary. The DCC will also mail a paper copy of the memo to the PI. PIs will be asked to notify the DCC when the memo is received.

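### For a single febrile UTI in months 8-12, the Table 1 footnote puts the interim DMSA scan at 1 year, while protocol 4.5 puts it 4 months after the UTI

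*Protocol*

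**What the plan says.** Protocol 4.5 (Outcome DMSA Scan) has two timing rules for the interim scan after a febrile UTI in the first year. If the UTI is in the first 8 months, the scan is at 12 months. If it is later, "If a febrile UTI occurs within 8-12 months, the interim DMSA scan will be scheduled 4 months from the interim UTI". When the interim scan shows new scarring, "that child will be considered a treatment failure and the interim DMSA scan will serve as the outcome scan".

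Table 1 has one rule. Its DMSA footnote, attached to the 12-month visit column, says "A DMSA scan will be performed at 1 year if there is an interim febrile UTI". The table marks no scan between the 12- and 24-month visits, and another footnote allows the 24-month scan to be omitted once an outcome scan exists.

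MOP 7.4.5.1 (Scheduling the 12 month DMSA) says "A DMSA scan will only be performed at 1 year if there is an interim febrile UTI". Protocol 5.3.2 and MOP 10.7.1 speak only of an interim 12-month scan. The rule for months 8-12 is stated in 4.5 alone.

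Two other groups have their own pathways in 4.5 and are not affected. A second febrile UTI triggers the treatment-failure pathway, with an outcome scan about 4 months after the last UTI. Children with baseline scarring of grade 3 or higher have a repeat scan at the time of any recurrent febrile UTI.

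**The concern.** The same child gets two different scan dates depending on which part of the protocol the site follows, and the scan concerned can define the primary endpoint. Under 4.5 an interim scan with new scarring becomes the outcome scan, and under 6.1.2 an indicated early scan that shows scarring is the primary outcome. The consequence is one-sided: a positive early reading may stand without a 24-month scan to check it, whereas a negative one is followed by the 24-month scan.

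The 4-month interval looks deliberate. The protocol uses about 4 months for post-failure outcome scans as well (4.5, 5.2, MOP 10.7.4). Section 1.2.2 reports that about 60% of acute inflammatory changes on DMSA resolve after prompt treatment, though it gives no time to resolution. A scan 1 to 3 months after the UTI shortens the interval that 4.5 sets.

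**Working it through.** **Scan dates.** Let m be the month of the single febrile UTI (baseline grade 2 or less).

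- Protocol 4.5: scan month = 12 if m ≤ 8, and m + 4 if m is in months 8-12.
- Table 1 footnote: scan month = 12, so the lag from the UTI is 12 − m.

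| UTI month m | Scan month, 4.5 | Lag, 4.5 | Scan month, Table 1 | Lag, Table 1 |
|---|---|---|---|---|
| 8 | 12 | 4 | 12 | 4 |
| 9 | 13 | 4 | 12 | 3 |
| 10 | 14 | 4 | 12 | 2 |
| 11 | 15 | 4 | 12 | 1 |
| 12 | 16 | 4 | 12 | 0 |

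The rules agree up to month 8 and then diverge by up to 4 months. If UTIs are spread evenly over months 8-12, the mean lag under Table 1 is 12 − 10 = 2 months instead of 4. The ±10-day contact window in protocol 4.4 cannot absorb a gap of this size.

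**Children exposed (assumption).** The documents give no febrile recurrence rate for this population. As a stand-in, take the reinfection figures of 4.6% and 7.2% in protocol Table 4 (a different cohort), treat all of them as febrile, take 6 months as that trial's follow-up, and assume a constant hazard.

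- Monthly hazard: h = −ln(1 − p6)/6. For p6 = 0.046, h = 0.00785; for p6 = 0.072, h = 0.01245.
- Probability that the first febrile recurrence falls in months 8-12: exp(−8h) − exp(−12h) = 0.0290 and 0.0440.
- Of 360 enrolled: 360 × 0.0290 = 10.4 and 360 × 0.0440 = 15.8.
- Allowing for 10% yearly attrition to month 10 (factor 0.9^(10/12)): 9.6 and 14.5.
- Wider range, 12-month febrile recurrence of 5% or 20%: probabilities 0.0164 and 0.0618, or 5.9 and 22.2 of 360.

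For any assumed rate these counts are upper bounds on exposure. They do not remove children with baseline grade 3 or higher or those with a second febrile UTI, and they include UTIs just after month 8, where the two dates barely differ. Only a child whose early scan is read as new scarring could be misclassified.

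**The case against.** The strongest reply is that Table 1 is a summary. Its footnote marks an otherwise unscheduled 12-month scan as conditional on a febrile UTI, 4.5 is the operative text, and the specific rule governs. That explains how the discrepancy arose. It does not remove it, because the footnote as written gives a date and the date is different.

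The reply is stronger for the MOP. Section 7.4.5.1 reads naturally as a condition, namely that there is no routine 1-year scan. Just before it, 7.4.5 says that participants with a committee-determined endpoint "prior to the 12 month follow-visit, will have different scheduling criteria for their repeat DMSA", with the coordinating centre supplying the details. Section 7.9.2 likewise puts participants with an assessed endpoint on a different imaging schedule and refers back to the protocol for it. Section 10.7.2 says a UTI determination "may result in a determination of treatment failure or the need for DMSA scheduling".

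A reader might infer that the coordinating centre never steps in for this child. MOP 10.7.3 says endpoint UTIs "will only be reported back to the clinical sites if the UTI now classifies the participant as a treatment failure", and the report described in 7.9.2 "notifies the Coordinator and Investigator of any endpoint determinations of treatment failure"; one febrile UTI does not make this child a failure. The documents do not support that inference. MOP 3.3.1 lists a febrile UTI separately from a treatment-failure determination as a reason for the centre to request a scan, and the deferrals above cover children with an adjudicated endpoint. What stands is narrower. No MOP text states the 4-month interval for this group, and the deferral in 7.4.5 depends on the endpoint being determined before the 12-month visit.

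On harm, the reply also has force. MOP 3.2.1 classifies a defect with preserved contour as acute pyelonephritis, not scar, and the baseline scan already relies on that distinction up to 112 days after the index UTI. This limits misreading of an early scan but does not make the two dates equivalent.

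**Conclusion.** The contradiction between the Table 1 footnote and protocol 4.5 holds for a child with baseline grade 2 or less and a single febrile UTI in months 8-12. Under the footnote the scan comes 0 to under 4 months after the UTI once the UTI falls after month 8; under 4.5 it comes at 4 months. The scan-date arithmetic rests on the text alone. MOP 7.4.5.1 is a weaker, secondary instance.

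The severity is modest. Exposure is about 10 to 16 of 360 children (6 to 22 on the wider range), on borrowed recurrence rates. A reader might infer that scarring proportions or the Aim 1 comparison are biased. The documents give neither the share of early scans that would be read as new scarring nor a time course for resolution, so neither the size nor the direction of an effect can be derived. Sample size and alpha are untouched.

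A reader might also take the 7-day urgency in MOP 3.3.1 and 3.4.2 to be meant only for baseline grade 3 or higher and want it restricted. Those sections state no such limit, so that change is not supported.

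**What to change.** Amend the Table 1 DMSA footnote, and for consistency MOP 7.4.5.1, to state both rules: interim DMSA at 12 months if a febrile UTI occurs in the first 8 months; 4 months after the UTI if it occurs in months 8-12. Leave MOP 3.3.1 and 3.4.2 as they are.

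The cost is two lines of wording and a numbered memo to the sites. No scans, visits or analyses are added.
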